3.3 Evaluation Criteria/Effectiveness

The CHANGE IN PRACTICE therapy regimen (which includes therapy with The MetaNeb® System) will be evaluated to determine if there is a decrease in the number of patients who experience Significant Postoperative Pulmonary Complications among the group of patients treated with The MetaNeb® System. Endpoints are described below:

Primary Endpoint:

Significant Postoperative Pulmonary Complication (PPC):

One or more of the following that occurs within seven (7) days of the post-surgical admission will be considered a Significant Postoperative Pulmonary Complication (PPC)

- **Patient Requires Prolonged Mechanical Ventilation:**

Defined as patient requirement for invasive mechanical ventilation (MV) for > 24 hours (after hour 24) post-operatively. This includes patients that require re-intubation and MV after hour 24, regardless of length of time on MV in the first 24 hours postoperatively.

Hill-Rom®	Evaluation of a practice change to include The MetaNeb® System to reduce postoperative pulmonary complications	Page 17 of 31
CBI	8 September 2016	Rev C Protocol #: CR-RR2015-001

- **Patient requires prolonged respiratory support for > 24 hours from post-surgical admission**
 - Requirement for non-invasive ventilation (NIV) above patient's baseline requirement after hour 24, or continuous positive airway pressure (CPAP) above patient's baseline requirement after hour 24.
 - Requirement for O₂ therapy > 40 % FiO₂ or > 5 LPM via NC (and above patient's baseline) after hour 24 postoperatively.
- **Diagnosis of Pneumonia Within Seven (7) Days**
 - Physician documented pneumonia AND
 - Radiologists report indicating pneumonia / new or expanded infiltrate AND
 - Elevated or low Temperature (> 38° C or < 36° C, or as defined by the site) and/or elevated white count above the upper level of normal as defined by the site
- **Readmission to ICU (or transfer to an elevated level of care) for pulmonary complications within seven (7) days of the post-surgical hospital admission**

Defined as readmission to the ICU within seven days of post-surgical hospital admission or readmission to an elevated care unit such as special care or ICU step-down unit after being moved to a lower (e.g. general care) floor (e.g. patient discharged from ICU on day 4 at 0800 is readmitted to the ICU before day 8 at 0800).

Secondary Endpoints:

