- **Requirement for invasive mechanical ventilation for > 48 hours within seven (7) days of the post-surgical hospital admission**

Defined as patient requirement for invasive mechanical ventilation (MV) for > 48 hours (after hour 48) post-operatively. This includes patients that require re-intubation after hour 48, regardless of length of time on MV in the first 48 hours postoperatively.
- **Requirement for respiratory support for > 48 hours within seven (7) days of the post-surgical hospital admission**

Respiratory support greater than the patient's baseline level for a period longer than 48 hours

 - Requirement for non-invasive ventilation (NIV) above patient's baseline requirement after hour 48 from post-surgical admission or continuous positive airway pressure (CPAP) above patient's baseline requirement after hour 48.
 - Requirement for O₂ therapy > 40 % FiO₂ or > 5 LPM pm via Nasal Cannula (and above patient's baseline) after hour 48 postoperatively.

Hill-Rom®	Evaluation of a practice change to include The MetaNeb® System to reduce postoperative pulmonary complications	Page 18 of 31
CBI	8 September 2016	Rev C

- **ICU Length of Stay (LOS)**

ICU length of stay, during initial hospital stay, will be determined by calculating the number of days/hours spent in ICU. The following will be documented:

- Time of admission to the ICU to actual time of initial discharge from the ICU during initial hospital stay
- Total ICU days/hours (includes readmissions) during initial hospital stay

- **Hospital Length of Stay (LOS)**

Hospital length of stay will be determined by calculating the number of days/hours spent in hospital. The following will be documented:

- Time of admission to time of discharge from the hospital (total days/hours)

- **Time on Mechanical Ventilation**

Time on mechanical ventilation, during the initial hospital stay, will be documented as follows:

- Time to initial extubation from time of initial intubation, if initial intubation was placed after surgery; or from time of post-surgical admission, if intubation was in place prior to start of surgery
- Total time on invasive mechanical ventilation - will be determined for each patient by calculating the total number of days/hours intubated and mechanically ventilated from the time of post-surgical admission until the time of initial hospital discharge.

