## 2 STUDY OBJECTIVES AND ENDPOINTS

### 2.1 Primary Objective and Endpoint

The primary objective of Stage I of this study is to estimate the incidence of postoperative pulmonary complications (PPC) in post-surgical patients receiving standard of care per hospital and respiratory care department procedures and policies.

The primary objective of Stage II of this study is to estimate the incidence of PPC in post-surgical patients receiving change in practice therapy regimen, which includes the addition of the MetaNeb® System to the standard of care per hospital and respiratory care department procedures and policies.

The primary endpoint at each stage is to evaluate the proportion of subjects who experience a significant PPC within seven (7) days of: post-surgical hospital admission (Stage I) or post-surgical hospital admission and MetaNeb® System administration (Stage II). A PPC is defined as having one or more of the following:

- 1. Patient requires prolonged mechanical ventilation for > 24 hours**  
Invasive mechanical ventilation (MV) for > 24 hours from post-surgical hospital admission (PSHA)
- 2. Patient requires prolonged respiratory support for > 24 hours from PSHA**

- Requirement for non-invasive ventilation (NI V) or continuous positive airway pressure (CPAP) above patient's baseline requirement, not related to obstructive sleep apnea (OSA), for > 24 hours from PSHA
- Requirement for O2 therapy > 40 % FiO2 or > 5 LPM via NC (and above patient's baseline), for > 24 hours from PSHA

3. **Diagnosis of Pneumonia within 7 days from PSHA**
  - Physician documented pneumonia, and
  - Radiologists report indicating pneumonia / new or expanded infiltrate, and
  - Elevated or low Temperature (> 38° C or < 36° C, or as defined by the site) and/or elevated white count above the upper level of normal as defined by the site
4. **Readmission to ICU (or transfer to an elevated level of care) for pulmonary complications**  
Defined as readmission to the ICU or readmission to an elevated care unit within 7 days from PSHA

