## 2.2 Secondary Endpoints

Secondary endpoints include the following:

1. **Requirement for invasive mechanical ventilation for > 48 hours**  
Invasive mechanical ventilation (MV) for > 48 hours within 7 days from PSHA
2. **Requirement for respiratory support for > 48 hours**
  - Requirement for non-invasive ventilation (NI V) above patient's baseline requirement after hour 48 from PSHA, or continuous positive airway pressure (CPAP) above patient's baseline requirement, not related to obstructive sleep apnea (OSA), for > 48 hours within 7 days from PSHA
  - Requirement for O2 therapy > 40 % FiO2 or > 5 LPM via nasal cannula (and above patient's baseline), for > 48 hours within 7 days from PSHA
3. **ICU Length of Stay**  
ICU length of stay, during initial PSHA, will be determined by calculating the number of days/hours spent in ICU. The following will be documented:
  - Time of initial admission to the ICU to actual time of initial discharge from the ICU
  - Total ICU days/hours (includes readmissions), during the initial hospital stay
4. **Hospital Length of Stay (LOS)**  
Hospital length of stay will be determined by calculating the number of days/hours spent in hospital. LOS will be calculated for initial and total hospital stays. The following will be documented:

- Time of admission to time of discharge from the hospital (total days/hours), for each hospital admission.

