### 6.1 Description of Analytical Methods

#### 6.1.1 Derived Variables

**Primary Endpoint:** occurrence of a postoperative pulmonary complication (PPC).

Stage I: during the 7 days post-surgery hospital admission (PSHA)

Stage II: during the 7 days PSHA. Event must occur after MetaNeb® administration.

For each subject, occurrence of a PPC will be set to yes if one or more of the four conditions below occur.

- i. **PPCflg1:** Patient Requires Prolonged Mechanical Ventilation beyond Hour 24 from PSHA.

Duration of invasive mechanical ventilation (IMV) is defined as IMV stop time minus IMV start time where:

IMV Start Time=date & time of the later of start of IMV or PSHA

IMV Stop Time=date & time of the earlier of stop of IMV or PSHA+7

If IMV is required on more than one occasion during the 7 days following PSHA, then the cumulative sum will be calculated.

$$\text{PPCflg1} = \begin{cases} 1 & \text{if the latest IMV stop time is more than 24 hours after PSHA} \\ 0 & \text{otherwise} \end{cases}$$

If IMV start date is available, but the start time is missing, then a clock time consistent with the earliest possible time of the day will be imputed, ex. Hour 00.00 or PSHA clock time.

If the IMV stop date is available, but the stop time is missing, then the IMV stop time will be taken as the assessment time.

- ii. **PPCflg2:** Patient Requires Prolonged Respiratory Support beyond Hour 24 from PSHA

- a) Duration of non-invasive MV (NIMV) is defined as NIMV Stop time minus NIMV start time. NIMV start and stop times are defined similarly to those of IMV.

Imputations for missing NIMV start or stop times will be used similarly to those of IMV.

- b) Duration of CPAP is defined as CPAP Stop time minus CPAP Start time.

- c) Duration of O2 therapy [if >40% FiO2 or >5 LPM via Nasal Cannula] will be calculated similarly.

Duration of respiratory support is defined as the sum of durations of NIMV, CPAP, and O2 therapy during the 7 days following hospital admission.

$$\text{PPCflg2} = \begin{cases} 1 & \text{if the latest NIMV, CPAP, or O2 therapy stop time} \\ & \text{is more than 24 hours after PSHA} \\ 0 & \text{otherwise} \end{cases}$$

- iii. **PPCflg3:** Diagnosis of pneumonia

- iv. **PPCflg4:** Readmission to ICU (or transfer to an elevated care) for PPC with 7 days of PSHA

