Secondary Endpoints derivations will follow similar logic as that of the primary endpoint, when calculating incidence of PPC > 48 hours. For time to initial extubation, if extubation occurred prior to hospital admission, then time to initial extubation will be set to zero.

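### The derivation of PPCflg2 in SAP 6.1.1 omits the above-baseline and OSA conditions of SAP 2.1, so the two sections can give different primary PPC counts

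*SAP*

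**What the plan says.** The respiratory-support component of the primary endpoint is described in three places.

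- **SAP 2.1, component 2.** NIV or CPAP counts only if above the patient's "baseline requirement, not related to obstructive sleep apnea (OSA), for > 24 hours from PSHA". Oxygen above the stated FiO2 or flow threshold counts only if it also exceeds baseline.
- **Protocol 3.3, primary endpoint.** The baseline condition applies to NIV, to "continuous positive airway pressure (CPAP) above patient's baseline requirement after hour 24", and to threshold oxygen. There is no OSA clause.
- **SAP 6.1.1, PPCflg2.** The flag is 1 "if the latest NIMV, CPAP, or O2 therapy stop time" lies more than 24 hours after post-surgical hospital admission (PSHA), and 0 in every other case. The oxygen input repeats the threshold ("LPM via Nasal Cannula] will be calculated similarly") without the baseline qualifier. NIV and CPAP enter with no qualifier. Any one of the four flags makes the patient a PPC.

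For the 48-hour respiratory-support endpoint, SAP 6.1.1 states "Secondary Endpoints derivations will follow similar logic as that of the primary endpoint". In SAP 2.2 the OSA wording comes after CPAP only ("baseline requirement, not related to obstructive sleep apnea (OSA), for > 48 hours within 7 days from PSHA"), whereas in SAP 2.1 it covers NIV and CPAP together. Protocol 3.3 again has only the baseline condition ("continuous positive airway pressure (CPAP) above patient's baseline requirement after hour 48").

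**The concern.** A programmer who codes 6.1.1 as written and one who codes 2.1 can obtain different primary counts from the same charts. No section says which governs.

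The affected patients can enrol. Of the five exclusions in Protocol 3.2.2, the only one about chronic support is chronic invasive ventilation. Home CPAP, home NIV and home oxygen do not exclude a patient, and a history of COPD is one of the routes into the high-risk group. SAP 6.1.5 and 6.1.6 plan to tabulate OSA history and pre-surgery NIV, CPAP and oxygen, but the flag uses none of them.

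Three consequences follow:

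- Each stage's PPC rate can be inflated by patients on their usual support.
- The Stage I rate may drive a change in sample size (SAP section 1), so the inflation could carry forward.
- If the share of such patients differs between stages, an apparent effect can arise in either direction. Consent is needed only in Stage II (Protocol 5.1), and only in Stage II does the SAP require "Event must occur after MetaNeb® administration". A difference is therefore possible, but the documents do not show one.

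**Working it through.** The documents give no power figure or event count to reproduce; SAP section 5 states that no formal sample size was determined. The check has two parts.

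**1. The rules applied to example patients.** All support below ends after hour 24, so only the qualifiers differ.

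| Patient | SAP 6.1.1 | SAP 2.1 | Protocol 3.3 |
|---|---|---|---|
| Home CPAP for OSA, unchanged, night 2 | 1 | 0 | 0 |
| New CPAP above baseline, given for OSA | 1 | 0 | 1 |
| Home oxygen at 6 LPM, unchanged | 1 | 0 | 0 |
| New NIV above baseline, not for OSA | 1 | 1 | 1 |
| No support | 0 | 0 | 0 |

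On these qualifiers 6.1.1 can only add events relative to 2.1. The second row shows that the SAP and the Protocol also disagree with each other on OSA.

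**2. How much the count could move.**

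Inputs:

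- *n* = 200 per stage (Protocol synopsis; SAP section 1).
- *p* = true Stage I incidence under 2.1: 5%, 10% or 15% (range in Protocol 3.5.1).
- Stage II true incidence *p*/2 (assumed halving of risk).
- *o* = share of patients without a 2.1 event whom 6.1.1 nevertheless flags. This is assumed; no document gives it.

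Formulas:

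- Observed rate = *p* + (1 − *p*)*o*, with *p*/2 in place of *p* for Stage II.
- Extra share of Stage I events = (1 − *p*)*o* / observed rate.
- Risk difference = (*p*/2)(1 − *o*).

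Example at *p* = 10%, *o* = 5%:

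- Stage I: 0.10 + 0.90 × 0.05 = 0.145.
- Stage II: 0.05 + 0.95 × 0.05 = 0.0975.
- Risk ratio: 0.0975 / 0.145 = 0.67.
- Extra share: 0.045 / 0.145 = 31%.

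| True rates | *o* | Observed rates | Risk ratio | Extra share, Stage I | Risk difference (points) |
|---|---|---|---|---|---|
| 5% v 2.5% | 1% | 5.95% v 3.48% | 0.58 | 16% | 2.475 |
| 5% v 2.5% | 5% | 9.75% v 7.38% | 0.76 | 49% | 2.375 |
| 10% v 5% | 0.5% | 10.45% v 5.48% | 0.52 | 4% | 4.975 |
| 10% v 5% | 1% | 10.90% v 5.95% | 0.55 | 8% | 4.95 |
| 10% v 5% | 5% | 14.50% v 9.75% | 0.67 | 31% | 4.75 |
| 15% v 7.5% | 1% | 15.85% v 8.43% | 0.53 | 5% | 7.425 |
| 15% v 7.5% | 5% | 19.25% v 12.13% | 0.63 | 22% | 7.125 |

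*Planned estimate.* The SAP presents a proportion with a 95% interval. At *p* = 10%, *o* = 5%, Stage I goes from 20/200 (10.0%, Wilson interval 6.6% to 14.9%) to 29/200 (14.5%, 10.3% to 20.0%). Wilson is an assumption, because the SAP names no interval method.

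*Power.* With a two-sided 5% pooled z-test (also assumed; the SAP names no between-stage test), power at 10% v 5% is 48% with no extra events. It falls to 45%, 43% and 31% at *o* = 0.5%, 1% and 5%.

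*Unequal shares, no true effect (10% in both stages).* With *o* = 2% in Stage I and 1% in Stage II, the rates are 0.10 + 0.90 × 0.02 = 11.8% and 0.10 + 0.90 × 0.01 = 10.9%, a risk ratio of 0.92. Reversing the shares gives 1.08.

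**The case against.** The strongest reply is that 6.1.1 was never meant to stand alone. PPCflg3 is only a label for pneumonia and cannot be programmed without the criteria in 2.1, so 6.1.1 could be read as timing logic laid over the definitions in 2.1. Protocol 3.5.2 also points to section 3.3 for the primary endpoint, and 3.3 requires support above baseline. On this view the gap is a drafting slip.

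That reading is possible, but the text does not secure it. Unlike PPCflg3, PPCflg2 is a complete rule with its own inputs and an explicit zero for everything else. It repeats the oxygen threshold while leaving out the qualifier attached to it in 2.1, and it does not refer back. The pointer to Protocol 3.3 confirms that 6.1.1 is the outlier on baseline, but it cannot settle OSA, where 3.3 and SAP 2.1 differ. The date visible in the SAP (16 August 2016) also precedes protocol Rev C (8 September 2016), so agreement with Rev C cannot be presumed.

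Several points on the other side stand:

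- The affected share is unknown, and at zero nothing changes.
- Patients with another PPC flag do not alter the primary count.
- Under equal shares the risk difference hardly moves; the dilution shows on the ratio scale, in power and in each stage's rate.
- Calling OSA-related events wrong would presume that SAP 2.1 is right, so they are described here only as extra relative to 2.1.
- A difference between stages is not demonstrated.

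**Conclusion.** The concern holds and must be fixed before programming. PPCflg2 as written does not implement the endpoint in SAP 2.1 or in Protocol 3.3, and the discrepancy reaches both the primary endpoint and the 48-hour respiratory-support endpoint. The contradiction itself needs no assumption.

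Its size cannot be derived from the documents. Each additional patient flagged adds 0.5 percentage points to a stage of 200 (1/200). Under the assumed halving of risk and an equal share in both stages, a 1% share moves the risk ratio from 0.50 to between 0.53 and 0.58 across the documented 5% to 15% range. A 5% share moves it to between 0.63 and 0.76, with 22% to 49% of Stage I events being ones that 2.1 would not count.

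**What to change.** 1. Write the above-baseline condition into PPCflg2 for NIV, CPAP and oxygen. Base it on the pre-surgery respiratory status and the daily milestone for return to baseline support, both recorded under Protocol 3.4.1.
2. Reconcile the OSA clause between SAP 2.1, SAP 2.2 and Protocol 3.3, including whether it covers NIV. Which version is right is for the sponsor and investigators to decide.
3. State whether the non-continuous CPAP recorded under Respiratory Treatments (Protocol 3.4.1) falls within the endpoint; neither Protocol 3.3 nor SAP 2.1 says.
4. Apply the agreed text identically in both stages, with a stated default where the baseline level or the CPAP indication is not documented. Carry the same text to the 48-hour endpoint.

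Settle this before Stage I is analysed; a choice made afterwards would leave the primary count open to selection.

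The cost is SAP wording, derivation code and one reconciliation of protocol and SAP. The drawback is data: Protocol 3.4.1 lists no field for CPAP indication and no explicit baseline settings, and a history of OSA does not show why a particular episode was given. Some chart queries and default classifications will be needed, mainly in retrospective Stage I.

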### **6.1.2 Accounting of Subjects**

Numbers (and percentage) of subjects enrolled in Stage I and Stage II, will be presented by site and overall.

### **6.1.3 Demographic and Baseline Characteristics**

Demographic and baseline data will be summarized separately for Stage I and II. Demographic data including age (years), age category (<35, 35-54, 55-64, ≥65), gender, race, ASA score, height, weight, BMI, and documented obesity (BMI≥30kg/m^2) will be summarized.

### **6.1.4 Time on Study**

The total number of days the subject is followed up will be summarized as continuous variable and categorized into 1-week intervals.

### **6.1.5 Medical History**

The pulmonary status will be tabulated, including the presence/absence of asthma, cystic fibrosis, bronchiectasis, COPD, neuromuscular disease, obstructive sleep apnea, other pulmonary conditions.

### **6.1.6 Pre-Surgery Respiratory Status**

Pre-surgery status of invasive mechanical ventilation, non-invasive mechanical ventilation, CPAP, and supplemental oxygen will be tabulated.

### **6.1.7 Post-Surgery Location**

The post-surgery location upon return to the hospital unit or floor (ICU, general care, etc.) will be tabulated.

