Number of Subjects:	The sample size will be approximately 400 patients, 200 in the retrospective STANDARD THERAPY group and 200 in the prospective CHANGE IN PRACTICE group.		
Study Population:	The study population consists of adult post-surgical patients who have undergone thoracic, aortic or upper abdominal surgery who are at high risk for PPCs.		
Inclusion/Exclusion Criteria:	
Inclusion Criteria:
 
Patients who meet all of the following criteria will be included in the study:
 
• Age \geq 18 years• Post-thoracic, -upper abdominal or -aortic surgery• Open surgical procedure• Incision at or above the umbilicus• High risk defined by:
• Documented ASA class \geq 3 
OR
 
• Documented ASA class 2 AND One or more of the following:
• Current smoker or smoking history within past 6 months• History of COPD• Documented obesity and/or BMI \geq 30 kg/m²• Age \geq 75 
Exclusion Criteria:
 
Patients who meet any of the following criteria will be excluded (or will be exited) from the study:
 
• Contraindication to Continuous High Frequency Oscillation (CHFO) therapy (e.g. untreated tension pneumothorax)• Minimally invasive, or “... scopic” procedure.• Spinal surgery involving a posterior approach• Surgery for organ transplant• Chronic invasive positive pressure ventilation (PPV)		

Statistical Methods:	
Descriptive summary statistics will be provided for demographics, the primary and secondary endpoints. Continuous data will be summarized with N, mean, median, standard deviation, min, and max. Categorical data will be summarized with the number and percent of patients in each category. Time to event data (ex. Time to readmission) will be summarized with methods appropriate for survival data including a Kaplan-Meier plot.
 
Ninety-five percent (95%) confidence interval will be computed for the primary endpoint, the incidence of significant postoperative pulmonary complications. Incidence rates for various demographic subsets, surgery types, and different population subsets may be presented as outlined in the statistical analysis plan document, to be published prior to study completion. Stage I and Stage II incident rates will be compared for the purpose of identifying any statistical associations that can be attributed to use of The MetaNeb® System.
		

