3.4.1 Study Observations Table Detailed Description

Hill-Rom®	Evaluation of a practice change to include The MetaNeb® System to reduce postoperative pulmonary complications			Page 20 of 31
	CBI	8 September 2016	Rev C	Protocol #: CR-RR2015- 001

Documentation of observations will be completed by study staff based on review of the patient's medical records. A detailed description of documentation requirements for each parameter is below.

Demographic Data: The following data will be recorded from the patient medical record: Age, Height, Weight, Race, Gender, ASA score, Documented obesity and/or $BMI \geq 30 \text{ kg m}^2$.

Medical History: Pulmonary history will be recorded from the patient medical record including: Asthma, Cystic Fibrosis, Bronchiectasis, COPD, Neuromuscular Disease, Other Pulmonary Condition(s), Obstructive Sleep Apnea

Pre-surgery Respiratory Status: Pre-surgery respiratory status such as Invasive Mechanical Ventilation, Non-invasive Mechanical Ventilation, CPAP, Supplemental oxygen will be recorded.

Post-Surgery Data (day 0): Following surgery, the albumin level (if available in the medical record) and surgery type will be recorded.

Location: The post-surgery location of each patient upon return to the hospital unit or floor (ICU, General Care, etc.) will be recorded. The patient's location during the first seven days, or until the time of discharge from the hospital, whichever occurs first, will also be recorded at regular intervals based on entries in the medical record.

Respiratory Status: The respiratory status of each patient, following surgery will be recorded. Respiratory status during the first seven days, or until the time of discharge from the hospital, whichever occurs first, will also be recorded at regular intervals based on entries in the medical record. Respiratory status will include documentation of the mode of support, the device in use and the settings.

Respiratory Milestones: Key respiratory milestones that occur each day will be recorded based on entries in the medical record. These include 1) extubation, 2) re-intubation, 3) return to baseline respiratory support, 4) Diagnosis of Pneumonia and 5) Readmission to the ICU or an elevated level of care. These milestones will be recorded for each day until discharge from the hospital, or through day seven (7) following the day of surgery, whichever occurs first.

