### **3 STUDY DESIGN**

This is a non-randomized facility level pre-post intervention study conducted in two stages for the primary purpose of evaluating the effect of The MetaNeb® System on postoperative pulmonary complications in high risk patients undergoing thoracic and abdominal surgeries. The study will be conducted in two to four (2-4) tertiary academic medical facilities in the US that have not previously used The MetaNeb® System in post-thoracic, post-aortic, or post-upper abdominal surgery patients. After assessing outcomes during a baseline period, therapy with The MetaNeb® System will be introduced and incorporated into the respiratory care treatment regimens and outcomes will be assessed after the change in practice.

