## 6 STATISTICAL ANALYSIS METHODS

The statistical software, SAS®, will be used for all summaries and statistical analyses.

Summary statistics will be used throughout. For continuous endpoints, the summary statistics will generally include: number of subjects with data (n), mean, standard deviation (SD), median, and range (Min, Max). For categorical endpoints, the summary statistics will generally include: number of subjects randomized and dosed, number with data, and the percentage of those with data in each category.

All statistical tests will be 2-sided with a type I error rate of 5%, unless otherwise specified.

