### **6.3 Analysis Methods – Primary and Secondary Endpoints**

#### **Primary Endpoint— Proportion of subjects who have a postoperative pulmonary complication**

The proportion of subjects who have a PPC within 7 days of post-surgery hospital admission will be presented with 95% confidence intervals.

Incidence of each of the 4 components that contribute to the primary endpoints, will also be presented.

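### Respiratory support in use at post-surgical admission is neither tabulated by stage nor accounted for in the crude PPC proportion, so a shift in it between stages could create or hide an apparent device effect

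*SAP*

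**What the plan says.** SAP section 3 describes the design: "This is a non-randomized facility level pre-post intervention study conducted in two stages". Protocol 3.5.2 says the stages will be compared to find associations attributable to the device.

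SAP 6.1.1 sets PPCflg1 to 1 "if the latest IMV stop time is more than 24 hours after PSHA". PPCflg2 applies the same rule to non-invasive ventilation, CPAP and high oxygen. The invasive ventilation start time is the later of the actual start and PSHA.

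SAP 6.1.3 to 6.1.7 list the descriptive tables. Two come close to the point:

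- SAP 6.1.6: "Pre-surgery status of invasive mechanical ventilation, non-invasive mechanical ventilation, CPAP, and supplemental oxygen will be tabulated".
- SAP 6.1.7: "The post-surgery location upon return to the hospital unit or floor (ICU, general care, etc.) will be tabulated".

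The first describes the patient before theatre, the second the unit the patient returns to. Neither gives the support in use on arrival.

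The data are collected. Protocol 3.4.1 states: "The respiratory status of each patient, following surgery will be recorded". It adds that mode, device and settings are documented, and Table 1 in both documents marks this item for the day of surgery. Protocol 3.1.2 has clinical data collected in both stages.

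For the primary analysis SAP 6.3 states: "The proportion of subjects who have a PPC within 7 days of post-surgery hospital admission will be presented with 95% confidence intervals". It adds the incidence of each of the four components, with no stratum or covariate.

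**The concern.** The 24-hour clock in PPCflg1 and PPCflg2 starts at PSHA. A patient who arrives intubated, on NIV/CPAP or on high oxygen meets the flag unless that support is withdrawn within 24 hours. A patient who arrives without it meets the flag only if support is started later. Two patients can thus enter the same clock from very different positions, for reasons settled in theatre.

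In a randomized trial this would balance on average. Here Stage I is a retrospective sample from the preceding year and Stage II a prospective, consented series. If extubation practice in theatre or the case mix changes between those periods, the crude PPC rate moves without any contribution from the device. The planned outputs do not show the share of patients arriving on each type of support, so a reader could not tell whether this had happened.

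**Working it through.** **Inputs from the documents.**

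- Sample size, Protocol Synopsis: "200 in the retrospective STANDARD THERAPY group and 200 in the prospective CHANGE IN PRACTICE group".
- Error rate, SAP section 6: "All statistical tests will be 2-sided with a type I error rate of 5%, unless otherwise specified".
- Expected PPC incidence under standard care, Protocol 3.5.1: 5% to 15%.
- There is no power figure to reproduce; SAP section 5 says no formal sample size determination was done.

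**Inputs not in the documents (assumed).** The share v arriving ventilated in each stage, the PPC risk a if ventilated on arrival, and the PPC risk b if not.

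**Formula with zero device effect.** Stage rate = v·a + (1 − v)·b. The apparent fall is (v1 − v2)·(a − b).

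**Illustration.** With a = 30%, b = 6% and v falling from 30% to 20%:

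- Stage I: 0.30 × 0.30 + 0.70 × 0.06 = 0.132.
- Stage II: 0.20 × 0.30 + 0.80 × 0.06 = 0.108.
- Apparent fall: 0.10 × 0.24 = 0.024, or 2.4 points.
- Standard error at 200 per stage: √[(0.132 × 0.868 + 0.108 × 0.892)/200] = 0.0325.
- 0.024/0.0325 = 0.74, so a two-sided 5% test would favor the device with probability about 11%, against 2.5% nominally.

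If v rises from 20% to 30% instead, the same arithmetic gives a 2.4-point apparent harm, which would cancel a real benefit of that size.

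**Range.** All rows have zero device effect, 200 per stage and a Stage I rate inside 5% to 15%.

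| Share ventilated, I → II | Risk if ventilated / not | PPC, I → II | Apparent fall (points) | Chance of significance favoring device |
|---|---|---|---|---|
| 20% → 15% | 20% / 5% | 8.0% → 7.25% | 0.75 | 5% |
| 30% → 20% | 30% / 6% | 13.2% → 10.8% | 2.4 | 11% |
| 20% → 10% | 40% / 5% | 12.0% → 8.5% | 3.5 | 21% |
| 20% → 10% | 50% / 5% | 14.0% → 9.5% | 4.5 | 29% |
| 20% → 10% | 10% / 10% | 10.0% → 10.0% | 0 | 2.5% |

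In the scenarios run, falls above 4.5 points (up to 8.25) arose only where the Stage I rate exceeded 15%, outside the protocol's range. The last row shows that there is no bias if arrival support does not affect risk.

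**Chance shifts are a separate matter.** Sampling alone can move the arrival share between stages by 1.96·√[2v(1 − v)/200], which is 5.9, 7.8 and 9.0 points at v = 10%, 20% and 30%. The crude interval already allows for this. In the illustration the Stage I outcome variance of 0.1146 splits into 0.1025 within strata and 0.30 × 0.70 × 0.24² = 0.0121 between them. Only a systematic shift is a bias.

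**What stratifying does.** In these scenarios the within-stratum rates are equal across stages, for example 30% against 30% and 6% against 6%, so a Mantel-Haenszel stage difference is zero.

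**The case against.** The strongest reply is that the plan is not blind to such a shift. ASA score, age and BMI are tabulated by stage (SAP 6.1.3), pulmonary history in 6.1.5, pre-surgery support in 6.1.6 and location in 6.1.7. Time to extubation is summarized and set to zero if extubation preceded admission. The four component incidences in SAP 6.3 would reveal a fall confined to prolonged ventilation. This stands: a reader might infer that no planned table would show a change in severity or extubation practice, and that would be wrong. These signals are nevertheless partial. An ICU bed does not say whether the patient is ventilated, a mean or median time to extubation does not give the share arriving ventilated, and a component incidence does not separate arrival mix from later course.

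Three further points stand:

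- PPCflg1 and PPCflg2 also capture re-intubation or support begun later, and pneumonia and ICU readmission are separate routes to a PPC. The documents give no figure for the weight of arrival support.
- Respiratory status is recorded by shift and no time of first MetaNeb treatment is fixed, so a first-shift entry could follow treatment.
- Stratifying on invasive ventilation alone would leave the NIV/CPAP and high-oxygen arrivals that feed PPCflg2 unadjusted.

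It is also fair to say that arrival support is one candidate covariate among several, such as site, ASA class and surgery type. What sets it apart is that the endpoint's own clock starts from it.

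**Conclusion.** The gap is real. Support in use at PSHA is tied by construction to two of the four primary components and is recorded in both stages, yet it is neither tabulated by stage nor accounted for in the primary proportion. A systematic shift in it could create or hide an apparent device effect, and the planned tables would disclose this only in part.

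The size is unknown. The 2.4-point illustration and the range of 0.75 to 4.5 points rest wholly on assumed shares, risks and shifts. The significance probabilities also presume a two-sided 5% test between stages, which SAP 6.3 does not specify.

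A reader might infer that arrival support is the main driver of the primary endpoint, that the recorded status always precedes device use, or that the result is biased in favor of the device. The documents support none of these. They give no risks by arrival status, fix no first-treatment time, and give no reason to expect a shift in one direction rather than the other.

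**What to change.** **SAP 6.1.7.** Add a by-stage table of respiratory support in use at PSHA, defined at PSHA and before any first MetaNeb treatment, in four categories: invasive ventilation; NIV/CPAP above baseline; oxygen above 40% FiO2 or above 5 LPM and above baseline; lower support. Invasive ventilation at PSHA can be derived from the SAP 6.1.1 times. That section imputes a missing start time to the earliest possible time, so imputed starts should be flagged: they could place a later intubation at PSHA.

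**SAP 6.3.** Beside the crude rates, as a supportive analysis, report PPC by arrival-support category and a Mantel-Haenszel stage difference with 95% CI across those categories. Specify in advance that they collapse to invasive ventilation yes/no if sparse.

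**Limits to state in the SAP.** Stratifying may remove any indirect effect through earlier extubation under the new practice; the crude rates keep it. It does not correct the other differences between stages: Stage II events count only after device administration (SAP 6.1.1), and untreated Stage II patients leave the ITT population (SAP 6.2).

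**Cost.** SAP wording, one table and one stratified estimate from data already recorded. SAP section 1 has Stage I analyzed before Stage II starts, so the Stage I arrival shares and risks could replace the assumed ones above.
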